2.3.2.3 Dose-blind Maintenance Treatment Period

After the 16-week Initial Treatment Period, subjects will enter the 40-week Maintenance Treatment Period. Treatment during the Maintenance Treatment Period will start with the first study drug administration on or after Week 16 and subjects will return to the clinic Q4W or Q8W through Week 56. The IMP will be administered in the clinic by sc injection at the time points specified in the schedule of study assessments.

Treatment during the Maintenance Treatment Period will be based on initial treatment per the following:

- Subjects in the bimekizumab 320mg Q4W treatment arm will continue to receive bimekizumab 320mg Q4W.
- Subjects in the bimekizumab 320mg Q4W/Q8W treatment arm will receive bimekizumab Q8W from Week 16 through Week 52.
- Subjects in the adalimumab treatment arm will receive bimekizumab 320mg Q4W from Week 24 to Week 52.

Subjects may receive placebo injections at certain visits in order to blind the IMP.

At the end of the Maintenance Treatment Period, all subjects enrolling in the open-label study will, after signing a new ICF, undergo the Week 56 study assessments and then receive their first dose of bimekizumab in the open-label study. All subjects not enrolling in the open-label study will have the Week 56 study assessments and will enter the SFU Period.

2.3.2.4 Safety Follow-Up Period

All subjects not continuing in the open-label study, including those withdrawn from IMP, will have a SFU Visit 20 weeks after their last dose of IMP.

2.3.2.5 Premature End of Treatment

Subjects withdrawing early from the study will undergo the PEOT Visit assessments and will enter the SFU Period.

2.3.3 Study duration per subject

For each subject, the study will last a maximum of up to 77 weeks, as follows:

- Screening Period: 2 to 5 weeks
- Double-blind, active-controlled Initial Treatment Period: 16 weeks
- Maintenance Treatment Period: 40 weeks
- Safety Follow-Up Period: a SFU Visit is planned 20 weeks after the last dose of IMP (for subjects not enrolling in the open-label study)

After the 40-week Maintenance Treatment Period, subjects will be allowed to enroll in an open-label study, in which case subjects will undergo the Week 56 study assessments before receiving their first open-label IMP dose. The SFU Visit will not be required for subjects who enroll in the open-label study.

The end of the study is defined as the date of the last visit of the last subject in the study.

2.3.4 Planned number of subjects and site(s)

Approximately 600 subjects will be screened in order to have 450 subjects randomized in the study. There will be approximately 150 subjects per treatment arm. The planned number of study sites is approximately 100. Every eligible subject who signs an ICF will be expected to be randomized.

2.3.5 Anticipated regions and countries

The regions planned for study conduct are Western Europe, Central/Eastern Europe, North America and Asia/Australia, with possible extension to other regions and countries.

2.4 Determination of sample size

A total of 450 subjects will be randomly assigned in a 1:1:1 ratio to the following treatment groups:

- Bimekizumab 320mg Q4W throughout the study (150 subjects)
- Bimekizumab 320mg Q4W/Q8W (ie, bimekizumab 320mg Q4W until Week 16, then bimekizumab 320mg Q8W from Week 16 through Week 52 (150 subjects)
- Adalimumab 80mg administered as an initial dose, followed by 40mg Q2W starting 1 week after the initial dose (ie, adalimumab will be administered according to the labeling recommendations) until Week 24, then bimekizumab 320mg Q4W from Week 24 to Week 52 (150 subjects)

When comparing bimekizumab to adalimumab, the assumed responder rates for PASI90 and IGA at Week 16 for the bimekizumab group are 75% and 85%, respectively. These estimates are based on the results of the Phase 2b PS0010 study. The PASI90 responder rates at Week 16 for adalimumab from the VOYAGE-1 and VOYAGE-2 studies were 50% and 47%, respectively (Blauvelt et al, 2017; Reich et al, 2017). Additionally, the IGA responder rates at Week 16 for adalimumab in VOYAGE-1 and VOYAGE-2 were 66% and 68%, respectively. For the purposes of these sample size calculations at Week 16, we assume a PASI90 responder rate and IGA responder rate for adalimumab of 50% and 68%, respectively.

The testing procedure described in protocol Section 14.3 indicates that the first test will be to demonstrate noninferiority to adalimumab for the co-primary variables of PASI90 and IGA at Week 16. If non-inferiority for both tests is demonstrated, then superiority to adalimumab will be tested.

Because the superiority evaluation is the more stringent test, sample size calculations are based on the testing of superiority to adalimumab for PASI90 and IGA at Week 16. Given these assumptions and a sample size of 150 subjects in the adalimumab arm and 300 subjects in the pooled bimekizumab arms, the power to detect a statistically significant difference between bimekizumab and adalimumab is >99% for PASI90 response and 97% for IGA response. This

assumes a 2-sided significance level of 0.05. Because both co-primary endpoints are highly powered independently, and because PASI and IGA response tend to be highly correlated, the overall power for achieving superiority on both co-primary endpoints is not calculated here.

Note that the non-inferiority testing procedure will be based on a 1-sided significance level of 0.025 and a non-inferiority margin of 10%. The power to demonstrate non-inferiority to adalimumab using the other assumptions described above is >99% for both PASI90 and IGA responses.

3 DATA ANALYSIS CONSIDERATIONS

3.1 General presentation of summaries and analyses

Statistical analysis and generation of tables, figures, subject data listings, and statistical output will be performed using SAS Version 9.3 or higher. All tables and listings will use Courier New font size 9.

Descriptive statistics will be displayed to provide an overview of the study results. For continuous variables, descriptive statistics will include number of subjects with available measurements (n), mean, standard deviation (SD), median, minimum, and maximum.

For categorical variables, the number and percentage of subjects in each category will be presented. Unless otherwise noted, the denominator for percentages should be based on the number of subjects included in the respective analysis set. Subjects with missing data can generally be accounted for using either of the following approaches:

- For summaries of demographics and Baseline characteristics: summarize percentages based on all subjects in the analysis set and include a “Missing” category (corresponding to subjects with missing data for the variable being summarized) as the last row in the list of categories being summarized.
- For summaries of efficacy and safety endpoints, unless otherwise specified: summarize percentages based only on those subjects with observed data for the variable being summarized. As the denominator may be different from the number of subjects in the analysis set being considered, the denominator should be displayed in the table. The general format for displaying this will be “n/Nsub (%)”

Percentages will be presented to 1 decimal place. If the percentage is 100%, do not present a decimal. If the percentage is 0, do not present the percentage. Typically, the % sign should be presented in the column header, but not with each individual value.

For bimekizumab PK concentrations, summary statistics will include geometric mean, geometric coefficient of variation (CV), 95% confidence intervals for geometric mean, arithmetic mean, SD, median, minimum, and maximum. All summaries of PK variables will be based on the observed values. No imputation will be used.

Decimal places for descriptive statistics will always apply the following rules:

- “n” will be an integer
- Mean, SD, and median will use one additional decimal place compared to the original data
- CV [%] will be presented with one decimal place

- Minimum and maximum will have the same number of decimal places as the original value.

Derived variables in general will display the mean, SD and median to 1 more decimal place than the variables used in the derivation. If the number of decimal places reported in the raw data is varied then use either the maximum raw number of reported decimal places or 3, whichever is the lowest, as a guide for the descriptive statistics.

Statistical tests of efficacy variables will be presented as two-sided p-values rounded to three decimal places. P-values less than 0.001 will be presented as “<0.001” and p-values greater than 0.999 will be presented as “>0.999.” Statistical comparisons will be two-sided and will be performed at the 0.05 level of significance.

A complete set of data listings containing all documented data as well as calculated data (e.g. change from Baseline) will be generated.

Per protocol, visit windows of ± 3 days from the first dose to Week 24 and ± 7 days from Week 28 to Week 56 are permissible. For the SFU Visit, visit window is ± 7 days from final dose. All by-visit summaries will contain nominal (i.e. scheduled) visits only. Unscheduled visits will not be mapped to scheduled visits except for some assessments that may occur within a 3-day time window of a scheduled visit. In that case, the assessment will be mapped to the corresponding scheduled visit and will be used for the analysis. This will only occur for some vendor data.

For missing PASI and IGA assessments at Week 16, available data from all visits (unscheduled or scheduled but without a planned assessment) within the 3 days window will be included.

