4.2.1.2 Handling missing data for the secondary efficacy variables

For secondary binary efficacy variables, missing data will be imputed using NRI as primary method. MI-MCMC/monotone regression and OC methods will be performed as sensitivity analysis.

For secondary continuous efficacy variables, MI-MCMC/monotone regression is the primary method for imputing missing data. If the imputation model cannot converge, last observation carried forward (LOCF) will be used. OC method will be performed as sensitivity analysis.

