4.2.1.5 Missing Data Overview and Summary

In summary, the approaches listed below will be used in this study for handling missing data for efficacy variables as appropriate:

- Non-responder imputation (NRI): Subjects who have missing data at the time point of interest are treated as though they did not respond to the treatment.
- Multiple Imputation (MI) – Markov Chain Monte Carlo (MCMC) / Monotone Regression: Using multiple imputation methodology, intermittent missing data are imputed based on the MCMC method, and monotone missing data are imputed using monotone regression. Note: for all analyses and summaries using MI, subjects with no baseline value will be excluded.
- Last observation carried forward (LOCF): Post-Baseline missing data are imputed by carrying forward the last available observation (including Baseline).

- Observed case (OC): Missing data are not imputed. Only subjects with available data who have not discontinued study treatment at the given time point are considered.

The following table depicts which missing data handling approaches should be used based on variable priority (primary, secondary, other) and variable type (responder, continuous, ordinal).

Table 4–1: Missing data handling approach by variable priority and type

Variable Priority	Variable Type	NRI	MI (MCMC/ Monotone Regression)	MI (MCMC/ Reference-based)	LOCF	OC
Primary	Responder	P	S ^a	n/a	S	S
Secondary	Responder	P	S ^a			S
	Continuous		P		B	S
Other	Responder	P				S ^{b, c}
	Continuous ^e		P		B	
	Ordinal					P ^d

P=Primary method, S=Sensitivity method, B=Backup method, NRI=Non-responder imputation, MI=Multiple imputation, MCMC=Markov Chain Monte Carlo, LOCF=Last observation carried forward, OC=Observed Case
Note: Backup method is only applicable when the primary method is unable to converge due to challenges with the imputation model.

^a Imputation method is applied on continuous data, and responder variable is derived from the continuous variable based on complete data set.

^b Only applies to by-visit summaries of variables that are in the multiplicity-controlled testing procedure.

^c Includes IGA response, PASI75, PASI90 and PASI100.

^d Includes Patient Global Assessment of PSO, IGA score and EQ-5D-3L responses.

^e For PASE, OC is the primary analysis method.

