8.1 Statistical analysis of the co-primary efficacy variables

8.1.1 Derivations of co-primary efficacy variables

For missing PASI and IGA assessments at Week 16, available data from all visits (unscheduled or scheduled but without a planned assessment) within the 3 days window will be included.

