8.2.2.1 PASI and IGA responses

For PASI100 response at Week 16 and 24, PASI75 response at Week 4, PASI90 and IGA response at Week 24, the stratified CMH test similar to the primary analysis will be implemented to test for superiority of bimekizumab over adalimumab.

The treatment comparisons at Week 24 for PASI100, PASI90 and IGA will be performed in three different ways using the following randomized treatment arms:

1. Bimekizumab Q4W and bimekizumab Q4W/Q8W combined vs adalimumab (testing H_7 , H_8 and H_9)
2. Bimekizumab Q4W only vs adalimumab (testing H_{10} , H_{11} and H_{12})
3. Bimekizumab Q4W/Q8W vs adalimumab (not part of the hierarchical testing sequence, these analyses will be exploratory and the p-values produced will be nominal)

Because all adalimumab subjects will receive bimekizumab treatment starting at Week 24, inferential comparisons against adalimumab after Week 24 will not be performed. PASI90 and IGA response at Week 56 will be summarized using descriptive statistics only.

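### A missing Week 16 PASI or IGA may be filled from another visit within 3 days, but the SAP gives no such rule at Weeks 4 and 24, which feed controlled secondary endpoints under the same visit window

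*SAP*

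**What the plan says.** SAP 3.1 carries the recovery rule, with the window counted in days: "For missing PASI and IGA assessments at Week 16, available data from all visits (unscheduled or scheduled but without a planned assessment) within the 3". SAP 8.1.1, on deriving the co-primary variables, has the same sentence, which begins "For missing PASI and IGA assessments at Week 16, available data from all visits". Both name Week 16 and no other visit. Because the rule is written for the assessment, it also serves PASI100 at Week 16.

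The general rule in SAP 3.1 is narrower: "Unscheduled visits will not be mapped to scheduled visits except for some assessments that may occur within a 3-day time window of a scheduled visit". The exception is then limited: "This will only occur for some vendor data". The SAP does not list which data these are. SAP 3.3 repeats that unscheduled visits are not mapped and mentions no exception.

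For a secondary endpoint left without a value, SAP 4.2.1.2 applies: "For secondary binary efficacy variables, missing data will be imputed using NRI as primary method". NRI is non-responder imputation.

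The endpoints concerned are tested against adalimumab under SAP 8.2.2.1: "For PASI100 response at Week 16 and 24, PASI75 response at Week 4, PASI90 and IGA response at Week 24, the stratified CMH test" is used. The visit window is ±3 days from first dose to Week 24. After that SAP 3.1 allows ± "7 days from Week 28 to Week 56 are permissible".

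**The concern.** The same measurement, taken equally close to its planned day, is treated differently by visit. Near Week 16 it replaces the missing value. Near Week 4 or Week 24 it is set aside and the subject is recorded as a failure. An observed response could therefore become an imputed non-response on an endpoint under familywise error control.

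Neither SAP 3.1, SAP 8.1.1 nor the list of changes to protocol-defined analyses (SAP 3.10) gives a reason for separating Week 16 from the other two visits. Elsewhere the SAP does accept such data: the time-to-PASI-response analysis in SAP 8.3.1.2 counts unscheduled visits.

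**Working it through.** **1. Are the endpoints in the controlled sequence?** Week 24 is explicit: SAP 8.2.2.1 assigns PASI100, PASI90 and IGA to H7–H9 (pooled bimekizumab) and H10–H12 (Q4W arm only). Week 4 has to be inferred, because Figure 4-1 is not reproduced. Three points agree:
- The co-primaries take H1–H4 (non-inferiority, then superiority) and Week 24 takes H7–H12. That leaves H5 and H6 for PASI100 at Week 16 and PASI75 at Week 4.
- Table 4-1 gives an observed-case analysis to variables in the multiplicity-controlled procedure, and its footnote reads "Includes IGA response, PASI75, PASI90 and PASI100".
- The nominal PASI75 tests in SAP 8.4 are at Weeks 1, 3 and 16, not Week 4.

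**2. Who could be affected?** With planned day = 7 × week and ±3 days, the windows are Week 3: 18–24, Week 4: 25–31, Week 5: 32–38, Week 23: 158–164, Week 24: 165–171. Neighbouring windows do not overlap, so a neighbouring visit held on time cannot supply the value. The affected subject missed the scheduled PASI or IGA but had one at an unscheduled visit, or at a neighbouring visit held outside its own window, within 3 days. Protocol 8.6 allows any assessment at an unscheduled visit but does not require PASI or IGA.

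**3. Size per subject.** Arms are 150 (adalimumab; Q4W only) and 300 (pooled bimekizumab).
- 1/150 = 0.67 points; 1/300 = 0.33 points.
- Assuming 0 to 3 affected subjects per arm, all true responders, the largest shift in one arm's rate is 3/150 = 2.0 points. This is not the shift in the treatment difference: with 3 in each of the three arms, pooled bimekizumab loses 6/300 = 2.0 points and adalimumab 3/150 = 2.0 points, and the difference does not move.

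**4. The plan's power figure.** SAP 2.4 states >99% (PASI90, 75% v 50%) and 97% (IGA, 85% v 68%) at Week 16, two-sided 0.05, 300 v 150. For IGA:
- pooled rate = (150×0.68 + 300×0.85)/450 = 0.793
- SE under the null = √[0.793×0.207×(1/150 + 1/300)] = 0.0405
- SE under the alternative = √[0.68×0.32/150 + 0.85×0.15/300] = 0.0433
- power = Φ[(0.17 − 1.96×0.0405)/0.0433] = 98.2%

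The unpooled version gives 97.5% and the continuity-corrected one 97.6%. PASI90 gives 99.95%. The stated figures are reproduced closely enough.

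**5. Illustration for Week 24.** The documents give no assumed rates at Week 4 or 24. Assume that the Week 16 rates hold at Week 24 and that a share m of responders in every arm is turned into non-responders, so each rate becomes p×(1−m):

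| m | IGA difference (points) | IGA power, 300 v 150 | IGA power, Q4W only, 150 v 150 | PASI90 power, 300 v 150 |
|---|---|---|---|---|
| 0 | 17.0 | 98.2% | 93.9% | 99.95% |
| 1% | 16.8 | 97.8% | 92.9% | 99.94% |
| 2% | 16.7 | 97.3% | 91.9% | 99.92% |
| 5% | 16.2 | 95.6% | 88.5% | 99.84% |

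For scale, m = 2% of IGA responders in a 150-subject bimekizumab arm is 0.02×0.85×150 = 2.6 subjects. If the loss fell only on bimekizumab, at 1% to 2%, pooled IGA power would be 96.9% to 95.0%.

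**6. Do the sensitivity analyses recover the value?** SAP 8.2.3 plans multiple imputation and observed-case analyses for these endpoints. The imputation uses scheduled assessment visits (SAP 4.2.1.6), and the observed-case analysis leaves the subject out. Neither scores the subject as a failure, and neither uses the recorded assessment.

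**The case against.** The strongest reply is that this is ordinary prioritisation: extra effort to recover data at the co-primary time point, and a simple pre-specified rule elsewhere. The affected group is narrow (step 2), the rule is the same in every arm, so losses partly cancel, and a recovered non-response changes nothing. Two sensitivity analyses avoid scoring these subjects as failures. The vendor-data exception might also cover them. All of this limits the size, and most of it stands. It gives no reason to set aside an observed value at Weeks 4 and 24. The exception is weak cover: if it included PASI and IGA, the separate Week 16 sentence would be largely redundant, and Protocol 9 has these scored by the investigator or another trained assessor.

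The Week 16 rule also cannot be copied unchanged to Week 24, because adalimumab subjects start bimekizumab there. That is correct, and the change needs a safeguard for it.

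A reader might add Week 56 to the list. The documents do not support that: PASI90 and IGA at Week 56 are secondary but only summarised descriptively (SAP 8.2.2.1), so no controlled test depends on them.

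**Conclusion.** The inconsistency is real for Weeks 4 and 24, and minor. A subject with an in-window unscheduled assessment at those visits would be scored a non-responder on a controlled endpoint, unless the vendor-data exception applies. Each such responder costs one arm 0.67 or 0.33 points. Under the assumptions in step 5, a 1% to 2% loss in all arms lowers the IGA difference by 0.2 to 0.3 points and Q4W-only power by 1 to 2 points.

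Two stronger readings are tempting. One is that subjects have in fact been misclassified; the documents report no such subject and give no count. The other is that the testing is biased; a loss that is equal across arms shrinks a true difference slightly and creates none under the null, and nothing in the documents points to unequal loss. The conclusion rests on the text as written and on the inferred place of PASI75 at Week 4 in the sequence.

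**What to change.** In SAP 3.1, extend the Week 16 sentence to PASI and IGA at Weeks 4 and 24, within ±3 days. At Week 24, admit only assessments made before the first dose given at or after Week 24, so that no adalimumab subject is scored after starting bimekizumab. State whether PASI and IGA count as vendor data. For consistency the rule may also be applied at Week 56, within its ±7-day window and before any open-label dose.

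The cost is one amended sentence, the existing Week 16 program logic, and an added pre-dose filter at Week 24 (with a wider window and an open-label filter if Week 56 is included). If the data have already been unblinded, leave the planned analysis as it is and report the extended rule as a labelled sensitivity analysis, with the number of subjects affected in each arm.

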3.2 Definition of Baseline values

A Baseline value for a subject is defined as the latest measurement for that subject up to and including the day of administration of first study medication, unless otherwise stated. If a Baseline assessment is taken on the same day as first administration of study medication, it is eligible to be used as the Baseline value, even in the case that the time of the assessment is recorded as taking place after the time of first study medication administration. This is considered acceptable as this measurement is still the best representation of the Baseline value of the given assessment since it is highly unlikely that the study medication could have an impact on any measurement in such a short period of time. However, such cases should be rare as study center personnel are instructed to do all assessments at the Baseline visit prior to administering study medication. One exception to this rule is plasma concentration. If Baseline plasma concentration is measured at a time after the first administration of study medication, then it should not be eligible to be considered as a Baseline plasma concentration. Such cases should be discussed with the quantitative clinical pharmacologist. If a Baseline measurement is missing or not collected, and a Screening value is available, the Screening value will be utilized as Baseline instead.

For subjects who start with adalimumab and switch treatment at the Week 24 Visit, an additional bimekizumab Baseline defined as the measurement at Week 24 will be used. If a Week 24 Visit measurement is missing, baseline will be the latest measurement prior to the first dose of bimekizumab. The variables listed below will also be summarized based on bimekizumab Baseline:

- PASI score

- DLQI
- Laboratory data (only in shift tables)

Note that for any laboratory value that occurs on the day of treatment switch, that lab value will be attributed and summarized for the treatment they were on previously. For subjects that switch from Adalimumab to Bimekizumab, the Baseline value is the laboratory value of the day of treatment switch.

Baseline values for component scores should be computed using components from the same visit where the relevant measurements were recorded prior to dosing. For example, if the Screening visit has all of the components, but the Baseline visit is missing one or more components, the Baseline value for the component score should be calculated using the Screening visit values.

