10.2.3.7 Hypersensitivity (including anaphylaxis)

- **Incidence and Event Rate of Anaphylactic Reaction TEAEs per 100 subject years by SOC, HLT and PT**

A separate table will be prepared based on the MedDRA anaphylaxis Algorithm (see Appendix 1) for acute anaphylactic events (reported on the same day as when an injection was administered or one day after). An AE glossary table will also be produced to summarize the MedDRA coding for these events. The glossary table will include the following fields: reported term, PT, LLT, HLT, and SOC.

- **Incidence and Event Rate of Hypersensitivity Reaction TEAEs per 100 subject years by SOC, HLT and PT**

A separate table will be prepared to summarize hypersensitivity events, identified using the SMQ “Hypersensitivity (SMQ)”. All TEAEs which code to a PT included in the Scope=Narrow search will be included in this table. An AE glossary table will also be produced to summarize the MedDRA coding for these events. The glossary table will include the following fields: reported term, PT, LLT, HLT, and SOC.

Furthermore, injection site reactions will be evaluated based on the any TEAE table (no separate table needed) by looking under the following HLTs: “Administration site reactions NEC” and “Injection site reactions”.

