For laboratory shift tables through initial and maintenance treatment period, the treatment groups BKZ 320mg Q4W, BKZ 320mg Q4W/Q8W, ADA/ BKZ 320 mg Q4W and BKZ Total will be presented. For subjects randomized to ADA, only data after the switch to Bimekizumab will be considered. The last value prior to the switch will be considered as baseline.

A by-subject listing of all laboratory data will be provided. This listing will be presented by treatment group and will include: center, subject identifier, age, sex, race, weight, visit, laboratory variable, result (with abnormal values flagged as “L” or “H” accordingly) and unit.

Markedly abnormal values are defined as those with a severity of Grade 3 and above based on the common terminology criteria for adverse events (CTCAE) criteria (U.S. Department of Health and Human Services 2010). Definitions of markedly abnormal values using the Grade 3 cut points are given in the tables below for age ranges of ≥ 17 years (Table 10–1 for markedly abnormal biochemistry values and Table 10–2 for markedly abnormal hematology values).

Tables summarizing markedly abnormal values should include a summary (counts and percentages) of markedly abnormal labs observed at any time while on treatment (ie, treatment-emergent markedly abnormal [TEMA]). For this summary, Baseline values and values observed more than 140 days after the last administration of study medication are not considered. The laboratory results classified as Grade 3 or Grade 4 will be summarized and listed separately.

Summaries in the ADA/BKZ arm will be provided to examine markedly abnormal labs occurring within 70 days and >70 days of the treatment switch. The time since the treatment switch is calculated as the number of days since the final dose of adalimumab. Only lab values recorded after the start of bimekizumab treatment will be included. 70 days was chosen as it is approximately equal to five half lives of adalimumab.

Table 10–1: Definitions of Markedly Abnormal Biochemistry Values

Parameter name	Conventional		Standard		Abnormal Designation
	Unit	Criteria	Unit	Criteria	
Creatinine	mg/dL	>3.0 x ULN	mmol/L	>3.0 x ULN	AH
Glucose	mg/dL	<40 >250	mmol/L	<1.7 >13.9	AL AH
Calcium	mg/dL	>12.5 <7.0	mmol/L	>3.1 <1.75	AH AL
Magnesium	mg/dL	>3.0 <0.9	mmol/L	>1.23 <0.4	AH AL
Potassium	mmol/L	>6.0 <3.0	mmol/L	>6.0 <3.0	AH AL
Sodium	mmol/L	>155 <130	mmol/L	>155 <130	AH AL

Table 10–2: Definitions of Markedly Abnormal Hematology Values

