10.4 Vital signs, physical findings, and other observations related to safety

10.4.1 Vital signs

The following vital signs variables should be summarized: systolic blood pressure (mmHg), diastolic blood pressure (mmHg), body temperature (°C) and heart rate (beats/min). The following summary will be provided:

- A summary of the absolute and change from Baseline value for each vital sign variable by treatment group and visit through initial and maintenance treatment period for the SS
- A summary of the number and percentage of subjects experiencing at least one markedly abnormal value for a vital sign variable as defined in Table 10–3, by treatment group, through Week 24 for the SS and through initial and maintenance treatment period for the BKZ set

Table 10–3: Definitions of Markedly Abnormal Blood Pressure Values

Parameter (unit)	Markedly Abnormal Low	Markedly Abnormal High
Systolic blood pressure (mmHg)	<90 and a decrease from Baseline of \geq 20	>180 and an increase from Baseline of \geq 20
Diastolic blood pressure (mmHg)	<50 and a decrease from Baseline of \geq 15	>105 and an increase from Baseline of \geq 15

A by-subject listing of all vital signs data should be provided. This listing should be presented by treatment group and will include: center, subject identifier, age, sex, race, weight, visit, vital sign variable and result (with abnormal values flagged as “L” or “H” accordingly).

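### SAP 3.2 lets a same-day reading taken after the first injection displace a pre-dose reading as Baseline, which can misclassify occasional safety values

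*SAP*

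**What the plan says.** In SAP 3.2 a Baseline value is "defined as the latest measurement for that subject up to and including the day of administration of first study medication". A same-day assessment is eligible "even in the case that the time of the assessment is recorded as taking place after the time of first study medication administration". The reason given is that "it is highly unlikely that the study medication could have an impact on any measurement in such a short period of time". The section adds that "such cases should be rare as study center personnel are instructed to do all assessments at the Baseline visit prior to administering study medication". It then states: "One exception to this rule is plasma concentration". No other variable is exempted, and nothing says which value is used when the same day has one reading before and one after the dose.

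The last paragraph of 3.2 works differently. Component scores are to be built from measurements of one visit taken before dosing.

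Four other places bear on the rule:

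- Protocol 5.6 and 8.2.1 put every Baseline Visit assessment before the injection. Protocol 8.6 allows any assessment at an unscheduled visit.
- SAP 10.3 counts markedly abnormal laboratory values from the first dose until 140 days after the last, and then says: "For this summary, Baseline values and values observed more than 140 days after the last administration of study medication are not considered".
- SAP Table 10-3 flags a low systolic pressure as "<90 and a decrease from Baseline of" 20 mmHg or more. The high flag needs more than 180 and a rise of at least 20.
- SAP 10.2.3.7 tabulates "acute anaphylactic events (reported on the same day as when an injection was administered or one day after".

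**The concern.** Followed literally, the word for the most recent value selects the post-dose reading whenever both exist on the first-dose day. That reading then leaves the post-Baseline record and becomes the reference for every later change, shift and change-based flag.

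The stated reason suits skin scores. It is weak for vital signs, laboratory values or an ECG repeated because something happened after the injection. Other parts of the SAP allow for effects that fast. The acute-reaction search covers the injection day, and its Category D terms in SAP 12.1 include hypotension and decreased blood pressure. SAP 10.2 attributes events on a treatment-switch day to the earlier treatment, but makes an exception for anaphylactic, hypersensitivity and injection-site events.

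At stake are the quantitative safety summaries of individual subjects, not a treatment comparison.

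**Working it through.** The plan gives no figure to reproduce, and the documents contain no first-dose-day readings. The check applies the plan's own rules to assumed values.

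**Blood pressure (Table 10-3).** Write B for Baseline and v for a reading. The low flag needs v < 90 and B − v ≥ 20. The high flag needs v > 180 and v − B ≥ 20.

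| Assumed systolic readings (mmHg) | B | Change, post-dose reading | Change, later reading | Flags |
|---|---|---|---|---|
| 120 pre-dose, 85 post-dose, 88 later | 120 | 85 − 120 = −35 | 88 − 120 = −32 | two low |
| same | 85 | 0 (it is Baseline) | 88 − 85 = +3 | none |
| 150 pre-dose, 185 post-dose, 190 later | 150 | 185 − 150 = +35 | 190 − 150 = +40 | two high |
| same | 185 | 0 (it is Baseline) | 190 − 185 = +5 | none |

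A later return to 120 would be reported as 120 − 85 = +35 against the post-dose Baseline.

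The result does not change for every affected subject. A later low reading v loses its flag only if the post-dose value is below v + 20 while the pre-dose value is not. With v = 88 the limit is 88 + 20 = 108. A post-dose Baseline of 108 or more leaves the later flag in place.

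**Laboratory values.** A post-dose sample on the first-dose day falls inside the on-treatment window of SAP 10.3. If 3.2 labels it Baseline, the later sentence of 10.3 removes it from the count. The two statements pull in opposite directions. Tables 10-1 and 10-2 use absolute or ULN-based limits, so later markedly abnormal values are still flagged. The CTCAE shift tables start from the Baseline grade and would move.

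**ECG.** Protocol 8.2.1 lists no ECG at the Baseline Visit, so the reference is normally the Screening tracing. An unscheduled post-dose ECG on the first-dose day would replace it as reference for the QTcF increases in SAP 10.4.3.

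**Treatment switch.** For laboratory shift tables, SAP 3.2 takes the value from the day of the switch, while SAP 10.3 takes the last one before the switch. They agree when the switch-day sample precedes the first bimekizumab dose. They can differ otherwise.

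**The case against.** The strongest reply is that the situation should hardly arise. All assessments are scheduled before the injection, no post-dose reading is planned on the first-dose day, and the SAP discloses the rule and calls such cases rare. The eligibility sentence can also be read as covering a scheduled assessment done late, not an unscheduled repeat. All of this limits frequency. It does not supply a tie-break, and the defining sentence still selects the most recent value.

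A reader might infer more than the documents support:

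- *That a first-dose reaction routinely becomes the Baseline.* This needs an additional or late same-day reading of the same variable.
- *That subjects re-measured after the injection are mostly those with a reaction.* Nothing says so. Protocol 8.6 names specimen collection or analysis problems as another reason for a repeat.
- *That first-dose abnormalities disappear.* Adverse events starting that day count as treatment-emergent whatever the Baseline value (SAP 10.2.1). The anaphylaxis search works on coded terms and injection dates. Laboratory and vital-sign data are all listed.
- *That each affected subject's classification reverses.* The 108 mmHg limit above shows otherwise.
- *That PASI90 or IGA response is at risk.* For PASI the component-score sentence already points to pre-dose values, and for both scores a change within hours is implausible.

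A further objection concerns the remedy. Preferring any Screening value over a late first-dose-day value would be wrong for efficacy scores. Screening can last up to 5 weeks and is also used to wash out prohibited medication (Protocol 5.2.1 and Table 7-2). A Screening PASI or IGA may therefore describe a different disease state. That objection stands, and the fix below respects it.

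**Conclusion.** The point holds as a wording defect in SAP 3.2. A post-dose vital-sign, laboratory or ECG value on the first-dose day can displace a pre-dose one as Baseline. That can erase a Table 10-3 flag, take a laboratory value out of the treatment-emergent count, and distort later changes and shifts for that subject.

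The size is small: few subjects, in a number that the documents do not allow one to compute, and no efficacy conclusion affected.

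The illustration rests on hypothetical readings. It also assumes that an unscheduled blood-pressure reading can count toward Table 10-3. SAP 10.3 provides for unscheduled values in laboratory tables that cover a period, but 10.4.1 is silent for vital signs. The loss of the later flag, at 88 or 190 mmHg, does not depend on that assumption if the later reading is a scheduled one.

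**What to change.** Reword SAP 3.2 along these lines:

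1. When a value recorded before the first dose exists on the first-dose day, the last such value is Baseline. A same-day value without a time counts as pre-dose.
2. For efficacy scores, a same-day value timed after dosing serves as Baseline only when there is no same-day pre-dose value. It then takes precedence over an older Screening score.
3. For vital signs, laboratory and ECG data, a value timed after the dose is post-Baseline. Baseline is the last pre-dose value, from Screening if necessary.
4. Bring the component-score sentence into line with items 1 and 2.
5. Use one definition of the switch-day laboratory Baseline in 3.2 and 10.3.

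The cost is a few sentences and a date-time comparison in the Baseline derivation. SAP 3.2 already assumes that assessment and dosing times are recorded. The protocol explicitly requires collection times for PK, biomarker and antibody samples (10.1, 10.2 and 11) but not for vital signs (12.3.3), so the untimed-value convention in item 1 is needed.
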